9.4 Secondary Endpoint Analysis

Patients that die in the study will be handled as worst case in all analyses.

To have an evaluation using all patients we will count an event as the type of need or worse (eg, patients with oxygen need; non-invasive ventilator need; ventilator need; or with death at time of evaluation will be counted as having data supporting oxygen need), and included in both denominator and numerator (refer to Section 8.5).

9.4.1 Time to a recovery state (Day 1 - Day 29; measured in days)

The time to recovery from Day 1 to Day 29 will be compared between treatment groups using a log-rank test; patients not in recovery at end-of study/withdrawal will be censored at last observed time point in the treatment period or at last time status was assessed if collected post treatment-withdrawal. Patients with death as outcome will be censored at the scheduled end-of-study Day 29. Data will be illustrated using Kaplan-Meier plots and the median time to recovery estimated if appropriate. Stratification in the model with respect to COVID disease severity will be done if the randomization outcome has sufficient numbers in each group with respect to these characteristics.

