	All-cause mortality at Days 29 and 60.	Clinical status assessed using the 7-point ordinal scale score.
		Death = 7-point ordinal scale score is equal to 7 or using a vital records search returns a death record, the date on the record will be the date of death.
	Proportion of patients alive and not in respiratory failure (invasive mechanical	Clinical status assessed using the 7-point ordinal scale score.
	ventilation or extracorporeal membrane oxygenation (ECMO)) at Days 7, 14 and 29.	The proportion of patients in each treatment arm that meet the definition of alive and not is respiratory failure.
		Alive and not in respiratory failure (invasive mechanical ventilation or ECMO) = 7-point ordinal scale score is equal to 1, 2, 3, 4 or 5.
	Proportion of patients needing re-hospitalization (post-dose Day 1 – Day 60).	Assessed following discharge: the eCRF question regarding re-hospitalization will be used at Day 29 and Day 60 follow-up contact.
		The proportion of patients in each treatment arm that meet the definition of re-hospitalization following discharge.
		Re-hospitalization = following their treatment with study medication and subsequent discharge from hospital, they were re-admitted to a hospital for COVID related issue(s).

pg. 15 Confidential

Endpoints		Definitions
	Total time of hospitalization	Clinical status assessed using the 7-point
	between Day 1 - Day 29 (measured in days).	ordinal scale score.
	(Hospitalized = # days where the 7-point ordinal scale score is equal to 3, 4, 5 or 6.
		Or 7-point ordinal scale score is equal
		to 7 if patient dies while hospitalized
		between Day 1-29.
	Change from baseline in 7-	Clinical status assessed using the 7-point
	point ordinal scale (Days 7, 14 and 29).	ordinal scale score.
		The mean change from baseline of the 7-point
		ordinal scale in each treatment arm as
	Total time on supplemental	assessed by the statistical analysis. Clinical status assessed using the 7-point
	oxygen (Day 1 - Day 29; measured in days).	ordinal scale score.
	. ,	Hospitalized patient supplemental oxygen = # days where the 7-point ordinal scale score is equal to 4, 5, or 6.
		 Or 7-point ordinal scale score is equal to 7 if patient dies while hospitalized between Day 1-29.
		Not hospitalized patient supplemental oxygen = # days where the 7-point ordinal scale score is equal to 2 (if required to have home oxygen).

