8.5 Missing Data

All attempts will be made to collect all data per protocol.

 The patients withdrawn from treatment will be followed up regarding their status according to the 7-point ordinal scale at Day 29 as far as possible (exceptions for patients with withdrawn consent or lost to follow-up) and this data will be the primary source for handling missing data in the study.

Any data point that appears to be erroneous or inexplicable based on clinical judgment will be investigated as a possible outlier.

• If data points are identified as outliers, sensitivity analyses may be performed to examine the impact of including or excluding the outliers. Any substantive differences in these analyses will be reported.

For survival analyses, patients with death as outcome will be censored at Day 29 (Day 60), unless the required event was reached prior to death. Patients who are lost to follow-up or terminate the study prior to Day 29 (Day 60) for other reason than death and prior to observing/experiencing the event will be censored at the time of their last observed assessment.

The only time to event analyses is the time to recovery.

For secondary endpoint analyses, the following imputation rules will be used for patients who are lost to follow-up, terminate early from the study, or do not have further outcome data available after discharge for any reason than death:

- Patients with no data collected at the actual time point of interest for other reason than
 death, the last assessment of their status prior to this time point will be used as a
 representative for that time point. Especially, if the patient's clinical status scale is 1 or 2
 at the last observed assessment, then the patient will be considered to be recovered
 through Day 29.
- For endpoints assessing total time (oxygen or non-invasive ventilator care), the status for patients with no data collected for other reason than death, will be assumed unchanged from last assessment of the score up to last day in the definition of the endpoint (Day 29). Thus, no extra days will be added for patients without oxygen or patients without non-invasive ventilator care at last assessment.
- Patients that die in the study will be handled as worst case in all the analyses, that is they are considered to be on oxygen need, non-invasive and invasive mechanical ventilator need for all time points following the death.

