- In analyses of oxygen need, patients in ventilator care (non-invasive or invasive mechanical) will be considered in oxygen need for the corresponding time period and patients with death as outcome will be considered in oxygen need for the remainder of the time period of evaluation.
- In analyses of non-invasive ventilator need, patients that require invasive mechanical ventilation will be considered also as having a non-invasive ventilator need. Patients with death as an outcome will be considered as having non-invasive ventilator need from

pg. 19 Confidential

time of death for the remainder of the time period of evaluation.

- In analyses of invasive mechanical ventilator need, patients with death as an outcome will be considered in invasive mechanical ventilator need for the remainder of the time period of evaluation
- The change from baseline in the 7-point ordinal scale will use the baseline score and the score at the endpoint using imputation for missing data as stated above, that is the last assessment of their status prior to this time point will be used.
- If the patient is discharged and no further hospitalization data are available, then the
 patient will be assumed to not have been readmitted. Thus, no additional imputed days
 on hospitalization will be added to the number of days recorded on available
 assessments for these patients.

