9.4.2.1 Sub-sets based on post-randomization outcome

Descriptive summaries of the proportion of patients as well as the duration of the worsening following initiation of study medication will be provided for these endpoints:

- Proportion of patients needing re-hospitalization (post-dose Day 1 Day 60).
 - Applies to the sub-set of patients that were randomized, treated with study medication and discharged from the hospital alive then re-admitted to the hospital for COVID-19 related treatment.
- Proportion of patients and duration of new oxygen use (post-dose Day 1 Day 29; measured in days).
 - Applies to the sub-set of patients that were randomized and treated with study medication but then had a new need for supplemental oxygen (score worsened to 4, 5 or 6).
 - Or those which improved during hospitalization (to 3) and then their clinical status worsened again (to 4, 5 or 6).
- Proportion of patients and duration of new non-invasive ventilation or high flow oxygen use (post-dose Day 1 - Day 29; measured in days).
 - Applies to the sub-set of alive patients that were randomized and treated with study medication but then had a new need for non-invasive ventilation or highflow oxygen use (score worsened to 5 or 6).
 - Or those which improved during hospitalization (to 3 or 4) and then their clinical status worsened again (to 5 or 6)

The total number of days with recorded use will be the sum of all reported days, regardless of whether the days occur consecutively or in disjoint intervals.

9.4.3 Change from baseline in 7-point ordinal scale (Days 7, 14 and 29).

Change from baseline in 7-point ordinal scale will be compared between treatments using ANCOVA models with treatment and COVID disease severity state as factors and baseline as a covariate. Estimated treatment difference with 95% confidence intervals and associated 2-sided p-value will be given. Sub-group analysis will only be performed for sub-groups with a minimum size.

9.4.4 Total time on supplemental oxygen (Day 1 - Day 29; measured in days).

The total number of days with recorded use will be the sum of all reported days, regardless of whether the days occur consecutively or in disjoint intervals. Results will be summarized by descriptive statistics including medians and quartiles by treatment arm and compared between treatment groups using Wilcoxon rank sum test. Patients that do not reach the specified score on any day will be counted as 0 days.

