Day 1 - Day 29	n		
-	Yes		
	No		

pg. 54 Confidential

⁽or discharge, whichever was first)
*7-point ordinal scale score = 1, 2, 3, 4 or 5. n = number of patients with recorded value

Table 14.2.11: Summary of Proportion of patients re-hospitalized following initiation of study medication and subsequent discharge (over 60 days), ITT

Proportion of Patients	Re-hospitalized	Enrolled (N=45)	Ensifentrine (N=30)	Placebo (N=15)
Day 1 - Day 60	ay 1 - Day 60 n			
	Yes			
	No			

n = number of patients with recorded value

Table 14.2.12: Duration of hospitalization from initiation of study medication (Day 1 - Day 29 (or discharge, whichever was first); measured in days), ITT

Days of hospitalization	Enrolled		Placebo p-value*
from Day 1	(N=45	(N=30)	(N=15)
Median (Q1 - Q3)			

^{*}Wilcoxon rank sum test

Hospitalized = # days where the 7-point ordinal scale score = 3, 4, 5 or 6.

Discharge = The patient is discharged and leaves the hospital alive.

pg. 56 Confidential

Table 14.2.13: Change from Baseline in 7-point Ordinal Scale at Days 7, 14, and 29, ITT

Change from 7-point Ordin	n Baseline in nal Scale	Enrolled (N=45)	Ensifentrine (N=30)	Placebo (N=15)
Day 7	n Mean (SD)	()	()	()
Day 14	n Mean (SD)			
Day 29	n Mean (SD)			

Computed from Day 1 scale minus Day 7, Day 14, and Day 29 scale accordingly (or discharge) (or discharge, whichever was first)

pg. 57 Confidential

Table 14.2.14: Total time on Supplemental Oxygen (Day 1 - Day 29; measured in days), ITT

Days of Suppl	emental Oxygen	Enrolled	Ensifentrine	Placebo
(Scale=4)		(N=45)	(N=30)	(N=15)
Day 1 - 29	Median (Q1 - Q3)			

Hospitalized patient: 7-point ordinal scale score = 4, 5, or 6. Or 7-point ordinal scale score is equal to 7 if patient dies while hospitalized between Day 1-29.

Not hospitalized patient supplemental oxygen = # days where the 7-point ordinal scale score is equal to 2 (if required to have home oxygen).

pg. 58 Confidential

Table 14.2.15: Total time of non-invasive ventilation or high flow oxygen use (post-dose Day 1 - Day 29 (or discharge, whichever was first); measured in days)

Days of non-invasive ventilation or High Flow Oxygen Use (Scale=5)		Enrolled (N=45)	l Ensifentrine (N=30)	Placebo (N=15)
Day 1 - 29	Median (Q1 - Q3)			

Non-invasive ventilation or high flow oxygen use = # days where the 7-point ordinal scale score is equal to 5 or 6. Or 7-point ordinal scale score is equal to 7 if patient dies while hospitalized between Day 1-29.

pg. 59 Confidential

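### The SAP promises worst-case handling of deaths in all analyses, but its rules for hospital, oxygen and NIV/high-flow days contradict each other and can score a death as a favourable result

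*SAP*

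**What the plan says.** The general rule is in SAP 9.4: "Patients that die in the study will be handled as worst case in all analyses". Section 8.5 repeats it and spells it out: "they are considered to be on oxygen need, non-invasive and invasive mechanical ventilator need for all time points following the death". For oxygen it adds that "patients with death as outcome will be considered in oxygen need for the remainder of the time period of evaluation". Neither sentence limits the place of death, and neither mentions days in hospital. Protocol 10.5.1 likewise treats deaths as in oxygen need and in ventilator need, with no limit of place and no rule for hospital days.

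Table 5 (SAP 7.2) is narrower. For total hospital days, oxygen days and NIV/high-flow days, score 7 enters the count under one condition: "Or 7-point ordinal scale score is equal to 7 if patient dies while hospitalized between Day 1-29".

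Shell 14.2.12, the output table for hospital days, is narrower still: "Hospitalized = # days where the 7-point ordinal scale score = 3, 4, 5 or 6". Score 7 is absent. Shells 14.2.14 and 14.2.15 repeat the Table 5 condition for oxygen and NIV/high-flow days.

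The analysis is the same for all three counts. From 9.4.4: "Results will be summarized by descriptive statistics including medians and quartiles by treatment arm and compared between treatment groups using Wilcoxon rank sum test". Sections 9.4.5 and 9.4.6 use the same wording. No section gives deaths a worst rank or a fixed maximum.

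**The concern.** In a rank test on days of need, fewer days is better. If a death stops the count, or adds only a few days, the patient who died ranks ahead of survivors who needed care for longer. That is the opposite of what a reader of 9.4 expects.

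The texts also conflict. Two programmers working from Table 5 and from Section 8.5 would derive different oxygen and NIV/high-flow days for the same patient, and one working from shell 14.2.12 would derive different hospital days again. The SAP does not say which text prevails.

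The direction of these endpoints matters because protocol 4.3 says the unpowered pilot will be read through trends across key endpoints.

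**Working it through.** The plan gives no figure to reproduce: no power, effect size or death rate is stated. The check applies the written rules day by day over Days 1 to 29.

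**Days added by a death on day d, where score 7 counts:** 29 − d + 1. Day 5 adds 25, Day 20 adds 10, Day 27 adds 3, Day 29 adds 1.

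**Constructed patients:**

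| Patient | Count | Table 5 | Section 8.5 | Shell |
|---|---|---|---|---|
| Discharged Day 5, dies at home Day 9 | Hospital days | 5 | no rule | 5 |
| Dies in hospital Day 5 | Hospital days | 4 + 25 = 29 | no rule | 4 |
| Oxygen Days 1–5, home without oxygen, dies at home Day 20 | Oxygen days | 5 | 5 + 10 = 15 | 5 |
| Same patient | NIV/high-flow days | 0 | 10 | 0 |
| Oxygen Days 1–5, home oxygen Days 6–11, dies at home Day 12 | Oxygen days | 5 + 6 = 11 | 11 + 18 = 29 | 11 |
| In hospital, never on NIV/high flow, dies Day 27 | NIV/high-flow days | 3 | 3 | 3 |

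Three things follow.

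1. Table 5 and Section 8.5 disagree on oxygen and NIV/high-flow days for deaths after discharge. Table 5 and shell 14.2.12 disagree on hospital days for deaths in hospital (29 against 4).
2. Under Table 5 a death can lower a patient's own count. The home-oxygen patient above would score 29 if alive on home oxygen to Day 29, but scores 11 by dying at home on Day 12.
3. A late in-hospital death ranks ahead of some survivors even where Table 5 and Section 8.5 agree. The Day 27 death scores 3 NIV/high-flow days, fewer than a survivor with 5.

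**Effect on the Wilcoxon comparison of hospital days.** All inputs except the arm sizes are assumed: 30 ensifentrine survivors, 12 placebo survivors, and 3 placebo patients discharged after 4, 5 or 6 days who then die at home by Day 29. Survivor stays are uniform on the whole days 3 to 11 in both arms.

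- Placebo survivor against ensifentrine survivor, probability of the longer stay (ties half): 0.50.
- Death with stay 4, 5 or 6 against an ensifentrine survivor: 1.5/9, 2.5/9 and 3.5/9, mean 2.5/9 = 0.278.
- As written: (12/15) × 0.50 + (3/15) × 0.278 = 0.400 + 0.056 = 0.456.
- Deaths ranked worst: (12/15) × 0.50 + (3/15) × 1 = 0.60.

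A simulation of 4,000 such trials gives means of 0.46 and 0.60. The arm with all the deaths looks better in 68% of trials as written, against 11% with worst rank. Two-sided p < 0.05 occurs in 7% and 16%.

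**A second illustration, oxygen days.** Survivor values run from 4 to 18 in both arms, and 3 deaths fall in the 30-patient arm. Mean ranks (lower is better; arm with deaths against the other) are:

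- post-discharge deaths by Table 5 (5 days): 22.4 against 24.2
- late in-hospital deaths (8 days): 22.7 against 23.6
- post-discharge deaths by Section 8.5 (15 days): 23.4 against 22.2
- worst rank: 23.8 against 21.5

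The arm with the deaths looks better in the first two cases. The p-values run from about 0.6 to 0.84.

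**The case against.** The strongest reply is that Section 8.5 defines worst case, and the definition is not worst rank. It is a status at each time point after death, and 9.4 refers the reader to 8.5. On that definition a late death adds few days because few remain, and under 8.5 a death never lowers the patient's own oxygen or NIV/high-flow count. SAP 7.2 also says further definitions are in Section 8, so Table 5 and 8.5 could be read together, with oxygen and ventilation need counted after a death at home.

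Much of this stands. The late-death ranking follows from 8.5 as defined and departs only from the plain sentence in 9.4. A reader might infer that the test generally rewards late deaths, but the documents do not support that. The Day 27 patient scores 3 NIV/high-flow days dead and 0 if alive and still without such support. In-hospital deaths after continuous need score the full 29 oxygen days, and early in-hospital deaths score at or near the maximum under Table 5.

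Two parts do not yield. The Table 5 condition on place of death is explicit and is repeated in shells 14.2.14 and 14.2.15, so reading it away is a choice the SAP does not make. And 8.5 has no rule for hospital days after a death, so it cannot repair that endpoint or shell 14.2.12.

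**Conclusion.** The inconsistency is real and should be resolved. The three day counts lack a single rule for deaths, and for hospital days in particular a death after early discharge scores as a short, favourable stay. The consequence is that an excess of deaths can be masked, or the apparent direction reversed, in these endpoints.

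The size is modest and conditional. The 0.46 against 0.60 rests on 20% placebo mortality, none on ensifentrine, and every death occurring after discharge. The documents give no expected death rate; with no deaths by Day 29 the problem has no effect. A reader might infer that two or three deaths would decide the comparison. The calculations do not show that: significance is uncommon under either rule (7% and 16%), and what changes is direction. Nor would deaths go unseen in the trial. They appear in all-cause mortality at Days 29 and 60, fail the endpoint of being alive and free of respiratory failure, and count as not recovered in the primary endpoint if they occur by Day 29. All analyses are declared exploratory.

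**What to change.** - In SAP 9.4.4 to 9.4.6, give every patient who dies on or before Day 29 the worst rank in the Wilcoxon test: tied with each other, worse than any survivor, whatever the date or place of death. Use a rank, not a numeric value such as 30 days, which is impossible in a 29-day window and would enter the planned medians and quartiles.
- Delete the clause "to 7 if patient dies while hospitalized" and its condition from the three day counts in Table 5.
- Amend Section 8.5 so that its death rules for these counts refer to the worst rank and include hospital days.
- Align shells 14.2.12, 14.2.14 and 14.2.15.
- Report medians and quartiles of days in survivors separately, with the number of deaths beside them in each arm.

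The cost is SAP wording and one derivation rule on data already collected. The downside is small: each Wilcoxon test becomes a ranked composite of death and days, which is close to what 9.4 says it intends, and the survivor rows are descriptive only because survival is a post-randomization outcome.

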9.4.2 Proportion of patients endpoint analyses

Secondary endpoints assessing proportion of patients fulfilling an event will be compared between treatments using a logistic regression model adjusting for treatment and COVID disease severity state. The difference between treatment arms will be expressed as a difference in proportions as measured by the Cochran Mantel-Haenzel (stratum)-weighted estimator based on the fitted logistic regression model. The delta method will be used to calculate the standard error for the difference and the associated confidence interval. For endpoints with a low number of events, the baseline disease state will be dropped from the model. In addition, the raw proportions per treatment group will be given. If 0 events in any of the groups only raw proportions will be given.

- Proportion of patients who are in a recovery state (Days 7, 14 and 60).
- Proportion of patients with improvement of one category using the 7-point ordinal scale (Days 7, 14 and 29).
- Proportion of patients with improvement of two categories using the 7-point ordinal scale (Days 7, 14 and 29).
- Proportion of patients in use of oxygen (Days 7, 14 and 29).
- Proportion of patients alive and not in respiratory failure (invasive mechanical ventilation or ECMO (Days 7, 14 and 29).

pg. 23 Confidential

- Proportion of patients receiving non-invasive ventilation (Days 7, 14 and 29).
- All-cause mortality.

9.4.2.1 Sub-sets based on post-randomization outcome

Descriptive summaries of the proportion of patients as well as the duration of the worsening following initiation of study medication will be provided for these endpoints:

- Proportion of patients needing re-hospitalization (post-dose Day 1 Day 60).
 - Applies to the sub-set of patients that were randomized, treated with study medication and discharged from the hospital alive then re-admitted to the hospital for COVID-19 related treatment.
- Proportion of patients and duration of new oxygen use (post-dose Day 1 Day 29; measured in days).
 - Applies to the sub-set of patients that were randomized and treated with study medication but then had a new need for supplemental oxygen (score worsened to 4, 5 or 6).
 - Or those which improved during hospitalization (to 3) and then their clinical status worsened again (to 4, 5 or 6).
- Proportion of patients and duration of new non-invasive ventilation or high flow oxygen use (post-dose Day 1 - Day 29; measured in days).
 - Applies to the sub-set of alive patients that were randomized and treated with study medication but then had a new need for non-invasive ventilation or highflow oxygen use (score worsened to 5 or 6).
 - Or those which improved during hospitalization (to 3 or 4) and then their clinical status worsened again (to 5 or 6)

The total number of days with recorded use will be the sum of all reported days, regardless of whether the days occur consecutively or in disjoint intervals.

9.4.3 Change from baseline in 7-point ordinal scale (Days 7, 14 and 29).

Change from baseline in 7-point ordinal scale will be compared between treatments using ANCOVA models with treatment and COVID disease severity state as factors and baseline as a covariate. Estimated treatment difference with 95% confidence intervals and associated 2-sided p-value will be given. Sub-group analysis will only be performed for sub-groups with a minimum size.

9.4.4 Total time on supplemental oxygen (Day 1 - Day 29; measured in days).

The total number of days with recorded use will be the sum of all reported days, regardless of whether the days occur consecutively or in disjoint intervals. Results will be summarized by descriptive statistics including medians and quartiles by treatment arm and compared between treatment groups using Wilcoxon rank sum test. Patients that do not reach the specified score on any day will be counted as 0 days.

9.4.5 Total time on non-invasive ventilator use (Day 1 - Day 29; measured in days).

The total number of days with recorded use will be the sum of all reported days, regardless of whether the days occur consecutively or in disjoint intervals. Results will be summarized by descriptive statistics including medians and quartiles by treatment arm and compared between treatment groups using Wilcoxon rank sum test. Patients that do not reach the specified score

pg. 24 Confidential

on any day will be counted as 0 days.

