6 INVESTIGATIONAL PLAN

6.1 Overall Study Design and Plan

The purpose of this study is to evaluate the effect of ensifentrine on the proportion of patients hospitalized with COVID-19 infection with recovery over 29 days.

This is a single center, randomized, double-blind, parallel group, placebo-controlled study to determine the efficacy and safety of ensifentrine 2 mg BID administered via pMDI added on to SoC treatment for COVID-19 infection compared to patients receiving SoC plus placebo.

Patients 18 to 80 years of age must be hospitalized with a confirmed diagnosis of SARS-CoV-2 infection confirmed by PCR test and displays at least one of the following: Respiratory rate greater than 24, new cough, new atypical chest pain, new dyspnea, oxygen saturation <97% at rest, chest x-ray with new changes consistent with COVID-19 related airspace disease.

Patients meeting criteria for inclusion and none of the criteria for exclusion at randomization will be randomized to receive study medication within 4 days of hospital admission until hospital discharge or up to 29 days of treatment, whichever comes first. Patients will be randomized 2:1 to receive one of the following study treatments:

- Treatment Arm 1 (n=30): Blinded ensifentrine (2 mg) pMDI BID + Standard of Care treatment for COVID-19 infection
- Treatment Arm 2 (n=15): Blinded placebo pMDI BID + Standard of Care treatment for COVID-19 infection

Randomized patients will receive blinded ensifentrine or placebo twice daily, approximately 12 hours apart in the morning and evening, through 29 days or until discharge from hospital, whichever is first. Patients will self-administer 4 actuations (puffs) pMDI observed by study staff at each dosing event.

During the treatment period, patients will undergo all assessments and procedures as outlined in the schedule of activities until hospital discharge. Patients completing treatment will complete a study contact (telephone or visit as required) within 4 to 10 days of discharge or early withdrawal. All enrolled patients will complete a telephone contact 26 to 32 days (Day 29) and 55-65 days (Day 60) following receipt of 1st dose of study medication for assessment of clinical status via the 7-point ordinal scale, need for re-hospitalization and vital status.

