6.4 Treatments Administered

Once eligibility is confirmed, patients will be randomized in a 2:1 ratio to one of two treatment arms listed in Table 1. Under the direction of study staff, randomized patients will self-administer 4 actuations (puffs) pMDI at each dosing event. Dosing will be performed twice daily approximately 12 hours apart in the morning and evening at approximately the same time each day.

Table 1. Clinical study RPL554-COV-201 treatment arms.

Treatment Arm	n	Treatment	
Treatment Arm 1	30	Blinded ensifentrine (2 mg) pMDI BID + SoC*	
Treatment Arm 2	15	Blinded placebo pMDI BID + SoC*	
Abbreviations: SoC= standard of care, pMDI= pressurized metered dose inhaler, BID= twice daily			
*SoC treatment for COV	*SoC treatment for COVID-19 infection based on established practices within UAB		

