8 GENERAL STATISTICAL CONSIDERATIONS

8.1 Sample Size

This is a pilot study and it is not powered based on any specific endpoint. Sample size has been set to minimize the number of patients exposed, but still large enough to give reliable estimates on the efficacy and safety of ensifentrine in the target population.

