8.2 General Principles

This is a double-blind, placebo controlled randomized pilot study which may inform on treatment effect for future studies.

All analyses are considered exploratory and hypothesis-generating. All tests will be two-sided at 5% significance level. Hypothesis tested for the primary endpoint will be if addition of ensifentrine to SoC for up to 29 days could increase the proportion of patients with recovery versus standard of care plus placebo. The status according to the 7-point ordinal scale of all patients regardless of treatment withdrawal will be followed up during the scheduled treatment period (Day 29) and at a follow-up Day 60, or as far as possible.

Secondary endpoints are tested independently and there will be no adjustment for multiple tests.

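### SAP 9.4.2.1 limits new NIV/high-flow use to living patients, against the SAP's own death rule, and gives readmission no denominator and no place for death

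*SAP*

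**What the plan says.** SAP 9.4.2.1 plans descriptive summaries, without a test, of readmission, new oxygen use and new NIV/high-flow use.

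- **New NIV/high flow:** "Applies to the sub-set of alive patients that were randomized and treated with study" medication. The event is a worsening to score 5 or 6. Score 7 (death) is not listed.
- **Readmission:** it covers patients who were treated and "discharged from the hospital alive then re-admitted to the hospital for COVID-19 related treatment". No sentence in the section states a denominator.

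The parent section, SAP 9.4, sets a general rule: "Patients that die in the study will be handled as worst case in all analyses". It adds that an event means the stated need or anything worse, names death among the worse states, and puts these patients in both numerator and denominator. SAP 8.5 treats patients who die as needing oxygen, NIV and invasive ventilation from death to the end of the evaluation period. It does not name readmission in that rule; it says only that a discharged patient with no later data is taken as not readmitted. Protocol 10.5.1 counts death as ventilator need.

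SAP Table 5 defines readmission as a proportion of the patients in each arm. The shell for Table 14.2.11 is headed "Summary of Proportion of patients re-hospitalized following initiation of study medication and subsequent discharge (over 60 days), ITT", with columns of N=45, 30 and 15 and a separate n row for patients with a recorded value. SAP Table 11 lists no table for new NIV/high-flow use.

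**The concern.** Both outcomes are secondary endpoints in protocol 3.2.2, and risk of deterioration is a secondary objective in protocol 3.1.2. Protocol 4.3 says this unpowered pilot will be read for trends across endpoints, so the by-arm percentages will carry weight even without a p-value.

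Death precludes readmission and is worse than NIV. A summary that removes deaths, or silently treats them as event-free, can make the arm with more deaths look better. For NIV, a programmer following 9.4.2.1 and one following 9.4 would reach different counts, each with textual support. For readmission, the text does not fix the base, and no rule says where a death before readmission belongs.

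**Working it through.** **Inputs.** Arm sizes come from SAP 6.1: "Treatment Arm 1 (n=30): Blinded ensifentrine (2 mg) pMDI BID", and 15 on placebo. The documents give no expected rate of death, NIV or readmission, and no power figure to reproduce ("This is a pilot study and it is not powered based on any specific endpoint"). All event counts below are therefore assumptions. The zero printed in the ensifentrine column of the Table 14.2.9 shell may be a placeholder and is not used. One patient is 1/30 = 3.3 percentage points on ensifentrine and 1/15 = 6.7 on placebo.

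**New NIV/high flow.** Assume 6/30 and 3/15 patients have the event (20.0% each) and nobody dies on placebo. On ensifentrine, k of the 6 later die and m others die without NIV. If *alive* means alive at the end of the period, the rate is (6 − k)/(30 − k − m). Death or new NIV in all 30 is (6 + m)/30.

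| k | m | Alive only | New NIV, all 30 | Death or new NIV, all 30 |
|---|---|---|---|---|
| 0 | 0 | 6/30 = 20.0% | 20.0% | 20.0% |
| 1 | 0 | 5/29 = 17.2% | 20.0% | 20.0% |
| 2 | 0 | 4/28 = 14.3% | 20.0% | 20.0% |
| 4 | 0 | 2/26 = 7.7% | 20.0% | 20.0% |
| 0 | 1 | 6/29 = 20.7% | 20.0% | 7/30 = 23.3% |
| 0 | 2 | 6/28 = 21.4% | 20.0% | 8/30 = 26.7% |

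Placebo stays at 20.0%. Deaths after NIV lower the alive-only rate; deaths without NIV raise it slightly. Deleting *alive* without adding score 7 gives the fourth column, which still omits the deaths that 9.4 would count.

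**Readmission, small illustration.** On placebo, 2/15 die in hospital and 1 survivor is readmitted. On ensifentrine there are no deaths and 3/30 are readmitted.

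- Discharged alive as base: 1/13 = 7.7% against 3/30 = 10.0%.
- ITT as base: 1/15 = 6.7% against 3/30 = 10.0%.
- Death or readmission, ITT: (2 + 1)/15 = 20.0% against 3/30 = 10.0%.

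Moving from the first base to the second does not change which arm looks better. Only counting death does.

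**Readmission, range.** Now put d in-hospital deaths on ensifentrine and none on placebo, with 20.0% readmitted on placebo. In the equal-risk case, every discharged patient has a 20% risk, so expected events are 0.2 × (30 − d). In the frail case, 10 of the 30 have a 40% risk and 20 have 10%, and all deaths fall in the frail, so expected events are 0.4 × (10 − d) + 0.1 × 20.

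| Case | d | Events | Discharged alive | ITT, death a non-event | Death or readmission, ITT |
|---|---|---|---|---|---|
| Equal | 1 | 5.8 | 20.0% | 19.3% | 22.7% |
| Equal | 3 | 5.4 | 20.0% | 18.0% | 28.0% |
| Equal | 6 | 4.8 | 20.0% | 16.0% | 36.0% |
| Frail | 1 | 5.6 | 19.3% | 18.7% | 22.0% |
| Frail | 3 | 4.8 | 17.8% | 16.0% | 26.0% |
| Frail | 6 | 3.6 | 15.0% | 12.0% | 32.0% |

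The discharged-alive base is distorted only if the patients who die differ in readmission risk. The ITT base with death as a non-event falls even when risks are equal.

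**The case against.** The strongest reply is that 9.4.2.1 is an openly labelled supplementary description in an exploratory trial, and that deaths are visible elsewhere. Mortality is tabulated at Days 29 and 60 (Table 14.2.9). The endpoint of being alive without respiratory failure treats death as failure. Table 5 counts in-hospital death in its own NIV/high-flow definitions. This stands, and it limits the harm to interpretation. It does not remove the contradiction, because a separate mortality table does not show which deaths left another table.

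It can also be said that *alive* means alive when NIV became necessary. A patient who had NIV and died later would then still count. The wording allows that reading but does not state it, and deaths without NIV would still be left out against 9.4.

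A reader might infer more than the documents support:

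- **That readmission will be computed among those discharged alive, or will always be 100%.** No denominator is stated. Because the described group contains the event, it may simply describe who counts as a case. Table 5 and Table 14.2.11 point to all patients per arm, though the n row leaves the percentage base open.
- **That conditioning on survival reverses the comparison.** In the illustration both bases favour placebo. The reversal comes from adding death to the endpoint.
- **That 9.4 already makes death a readmission event.** SAP 8.5 spells out the death rule for oxygen and ventilation only, so death or readmission is an added summary.
- **That two readmission rates will be published.** Table 11 plans a single readmission table.

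**Conclusion.** The point holds in two parts of different strength. For new NIV/high flow there is a direct contradiction: 9.4.2.1 restricts the summary to living patients with score 5 or 6, while 9.4, 8.5 and protocol 10.5.1 count death as need. Under the assumed counts, the alive-only rate ranges from 7.7% to 21.4% where the true frequency of new NIV is 20.0%, so both size and direction depend on who dies. For readmission the defect is an unstated denominator and no assigned place for death. On either candidate base, readmission alone can favour the arm with more deaths, and changing the base does not cure that.

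With no deaths the distortion is nil, but the contradiction and the undefined base remain. No hypothesis test is affected.

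**What to change.** In SAP 9.4.2.1, state the numerator and denominator of each summary and use all ITT patients as the base.

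- **New NIV/high flow:** delete *alive* and add score 7, so that the summary becomes death or new NIV/high flow by Day 29, in line with 9.4. Both edits are needed. Say that the duration summary follows the 8.5 rule for days after death. Add the table that Table 11 lacks.
- **Readmission:** keep the protocol endpoint. Beside it, add a row for death or readmission by Day 60, the number discharged alive, and the number without contact, since 8.5 takes the last group as not readmitted.

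The cost is SAP wording and two or three descriptive rows. No new data are needed: the ordinal score, vital status and re-hospitalization status are already in the Schedule of Activities. The drawback is a composite that mixes death with a less severe event, which is why readmission alone should stay visible next to it.
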